10.1.4. Data Protection

Participants will be assigned a unique identifier by the sponsor. Any participant records or datasets that are transferred to the sponsor will contain the identifier only; participant names or any information that would make the participant identifiable will not be transferred.

The participant must be informed that his/her personal study-related data will be used by the sponsor in accordance with local data protection law. The level of disclosure must also be explained to the participant who will be required to give consent for their data to be used as described in the informed consent.

The participant must be informed that his/her medical records may be examined by Clinical Quality Assurance auditors or other authorized personnel appointed by the sponsor, by appropriate IRB/IEC members, and by inspectors from regulatory authorities.

10.1.5. Committees Structure

Internal Safety Data Review Committee

Participant safety will be continuously monitored by the sponsor's internal safety data review committee (ISDRC) in a blinded manner, which includes safety signal detection at any time during the study.

This committee will be composed of the following members:

- Safety Physician
- Clinical Safety Scientist
- Biostatistics Lead
- Sponsor Medical Monitor
- Clinical Research Organization Medical Monitor

Blinded safety data from the study will be reviewed on an ongoing basis as part of routine safety data review with regular review of aggregate blinded safety information within monthly JZP150 ISDRC meetings. The ongoing review of safety data will include the following elements:

- Abnormal, clinically significant changes in the physical examination [REDACTED], will be recorded as TEAEs and reviewed.
- Changes from Baseline in vital signs.
- Clinical laboratory tests (chemistry, complete blood count, urinalysis [REDACTED]
[REDACTED].
- ECG data, to include an evaluation of clinically relevant changes from Baseline.
- TEAEs with attention to the development and frequency of previously unidentified TEAEs as well as identified TEAEs and the following AEOSIs:
 - Severe neurological events
 - Psychiatric events (eg, behavioral/cognitive changes, suicidal ideation or behavior)
 - Vision changes (eg, blurred vision)
 - Hepatic-related events (new right upper quadrant pain, hepatomegaly, tenderness, jaundice, serum chemistry abnormalities)
 - [REDACTED]

All blinded safety data collected will be summarized and reviewed by ISDRC for agreement of next steps.

If adverse safety trends are detected that may constitute a risk to study participants prior to the monthly ISDRC meetings, an ad hoc Safety Management Team (SMT) meeting will be urgently

convened to evaluate the information and determine actions that should be undertaken up to and including termination of the clinical study ([Section 10.1.9.2](#)).

Case unblinding may be performed for above reviews if necessary, including but not limited to participants meeting protocol participant stopping criteria (see [Section 7](#)). The SMT will include membership distinct and separate from the blinded study team and its structure and standard operating procedures will be specified in a charter in accordance with Jazz Pharmacovigilance policies.

10.1.6. Dissemination of Clinical Study Data

As the sponsor of the study, Jazz Pharmaceuticals is solely responsible for disclosing results on ClinicalTrials.gov, EudraCT, and other public registries in accordance with applicable global laws and regulations. By signing this protocol, the investigator acknowledges that all posting requirements are solely the responsibility of the sponsor and agrees not to submit any information about the study or its results.

10.1.7. Data Quality Assurance

Investigators and site staff will be trained on protocol procedures and electronic case report form (eCRF) completion prior to enrolling participants in the study.

All participant data relating to the study will be recorded on printed or eCRF unless transmitted to the sponsor or designee electronically (eg, laboratory data). The investigator is responsible for verifying that data entries are accurate and correct by physically or electronically signing the CRF.

Guidance on completion of CRFs will be provided in data handling and entry guidelines.

The investigator must permit study-related monitoring, audits, IRB/IEC review, and regulatory agency inspections and provide direct access to source data documents.

Monitoring details describing strategy (eg, risk-based initiatives in operations and quality such as Risk Management and Mitigation Strategies and Analytical Risk-Based Monitoring), methods, responsibilities and requirements, including handling of noncompliance issues, and monitoring techniques (central, remote, or on-site monitoring) are provided in the Monitoring Plan.

The sponsor or designee is responsible for the data management of this study, including quality checking of the data.

The sponsor assumes accountability for actions delegated to other individuals (eg, Contract Research Organizations).

Records and documents, including signed ICFs, pertaining to the conduct of this study must be retained by the investigator or institution/site as applicable, for the period of time established in the clinical study agreement entered into by the investigator's study site unless local regulations or institutional policies require a longer retention period. No records may be destroyed during the retention period without the written approval of the sponsor. No records may be transferred to another location or party without written notification to the sponsor.

10.1.8. Source Documents

Source documents provide evidence for the existence of the participant and substantiate the integrity of the data collected. Source documents are filed at the investigator's site.

Data reported on the CRF or entered in the eCRF that are transcribed from source documents must be consistent with the source documents or the discrepancies must be explained. The investigator may need to request previous medical records or transfer records, depending on the study. Also, current medical records must be available.

Definition of what constitutes source data can be found in data handling and entry guidelines.

The investigator must maintain accurate documentation (source data) that supports the information entered in the CRF.

Study monitors will perform ongoing source data verification to confirm that data entered into the CRF by authorized site personnel are accurate, complete, and verifiable from source documents; that the safety and rights of participants are being protected; and that the study is being conducted in accordance with the currently approved protocol and any other study agreements, ICH GCP, and all applicable regulatory requirements.

10.1.9. Study and Site Start and Closure

10.1.9.1. First Act of Recruitment

The study start date is the date on which the first participant has the first visit.

10.1.9.2. Study/Site Termination

The sponsor or designee reserves the right to close the study site or terminate the study at any time for any reason at the sole discretion of the sponsor. Study sites will be closed upon study completion. A study site is considered closed when all required documents and study supplies have been collected and a study site closure visit has been performed.

Administration of the study agent will be temporarily suspended by the SMT upon the occurrence of any of the following:

- Unexpected SAEs within the same SOC or similar in nature are reported by 2 or more participants on active study intervention with a plausible relationship to study intervention administration.
- 1 or more participants on active study intervention meets Hy's Law Criteria as defined in [Appendix 7](#).

Based on the sponsor review and evaluation of the aforementioned safety events, the study may be restarted or terminated.

The investigator may initiate study site closure at any time, provided there is reasonable cause and sufficient notice is given in advance of the intended termination.

Reasons for the early closure of a study site by the sponsor or investigator may include but are not limited to:

For study termination:

- Sponsor makes a business decision to stop the study.
- Study stopping criteria are met and following investigation, the sponsor decides to stop the study.
- Ongoing evaluation of study safety data suggests that the benefit-risk profile suggests stopping the study.

For site termination:

- Failure of the investigator to comply with the protocol, the requirements of the IRB/IEC or local health authorities, the sponsor's procedures, or GCP guidelines
- Inadequate or no recruitment (evaluated after a reasonable amount of time) of participants by the investigator
- Total number of participants included earlier than expected

If the study is prematurely terminated or suspended, the sponsor shall promptly inform the investigators, the IECs/IRBs, the regulatory authorities, and any contract research organization(s) used in the study of the reason for termination or suspension, as specified by the applicable regulatory requirements. The investigator shall promptly inform the participant and should assure appropriate participant therapy and/or follow-up.

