20. Use of prohibited prescription and/or non-prescription drugs and other products. See [Section 6.8](#) for details.

Prior/Concurrent Clinical Study Experience

21. Prior exposure to JZP150 (previously known as PF-04457845) or participation in a prior clinical trial of PF-04457845.
22. Received an investigational drug in the past 30 days or 5 half-lives prior to Screening (whichever is longer), or plans to use an investigational drug (other than the study intervention) during the study.

Diagnostic Laboratory Assessments

23. Clinically significant abnormal laboratory values as assessed by the investigator (clinical chemistry, hematology, and urinalysis), including creatinine clearance (CrCL) < 60 mL/min per Cockcroft-Gault Equation, total bilirubin $> 1.5 \times$ upper limit of normal (ULN) (isolated), alanine aminotransferase (ALT) or aspartate aminotransferase (AST) $> 2 \times$ ULN (isolated), or ALT or AST $> 1 \times$ ULN and have a total bilirubin $> 1 \times$ ULN. An isolated total bilirubin $> 2 \times$ ULN attributable to known Gilbert syndrome is not exclusionary. Note: Screening laboratory tests may be repeated 1 time.
24. Urine drug screen positive at screening for cocaine, amphetamines, methamphetamine, barbiturates, benzodiazepines, opioids, methadone, THC, MDMA, PCP, LSD, except for prescribed drugs at Screening that will be washed out prior to Baseline.
25. Positive alcohol breath test at screening.

Other Exclusions

26. Does not agree to refrain from consumption of food/food products containing seville oranges, grapefruit, pomelos, tangelos, or grapefruit hybrids from 2 weeks before the start of study intervention until after the final dose.

27. Allergy or sensitivity to any ingredients in the study intervention formulation or placebo.
28. Any other condition and/or situation that causes the investigator or medical monitor to deem the participant unsuitable for the study.

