7.1.1. Liver Chemistry Stopping Criteria

Discontinuation of study intervention for abnormal liver tests is required by the investigator when a participant meets one of the conditions outlined in [Appendix 7](#) or in the presence of abnormal liver chemistries not meeting protocol-specified stopping rules if the investigator believes that it is in best interest of the participant.

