APPENDIX 3. CLINICAL LABORATORY TESTS

The tests detailed in [Table 6](#) will be performed by the central laboratory, with the exception of urine pregnancy, urine dipstick for drug screen (with the exception of the screening visit during which urine drug screen will be done by the central lab), and breath alcohol tests, which will be performed locally.

Participants are required to fast for safety laboratory tests at the Baseline Visit (Visit 2), Week 1 (Visit 3), Week 4 (Visit 5), Week 12 (Visit 9), Early Discontinuation (Visit 10), if applicable, and Safety Follow-up Visit (Visit 12). Participants are not required to fast for laboratory tests at the Screening Visit or Week 8 (Visit 7).

Local laboratory results are only required in the event that the central laboratory results are not available in time for either study intervention administration and/or response evaluation. If a local sample is required, it is important that the sample for central analysis is obtained at the same time. Additionally, if the local laboratory results are used to make either a study intervention decision or response evaluation, the results must be recorded.

Protocol-specific requirements for inclusion or exclusion of participants are detailed in [Section 5](#) of the protocol.

Additional tests may be performed at any time during the study as determined necessary by the investigator or required by local regulations.

Investigators must document their review of each laboratory report.

Table 6: Protocol-Required Safety Laboratory Tests

Laboratory Tests	Parameters				
Hematology ^a	Platelet Count	RBC Indices: MCV MCH Reticulocytes (count, absolute)	WBC count with Differential: Neutrophils Lymphocytes Monocytes Eosinophils Basophils		
	RBC Count				
	Hemoglobin				
	Hematocrit				
Clinical Chemistry ^{ab}	Albumin	ALP ^c	ALT/ SGPT	AST/ SGOT	
	BUN	Calcium	CO ₂	Chloride	
	Creatinine	Creatine kinase	GGT	Glucose	
				HbA1c (Screening and Week 12 only)	
	Lactate dehydrogenase	Phosphorus	Potassium	Sodium	
	TSH (Screening only)	Total and direct bilirubin	Total cholesterol	Total protein	

Laboratory Tests	Parameters			
	Triglycerides	Uric acid	High-density lipoprotein cholesterol	Low-density lipoprotein cholesterol
	LH (males only)	FSH (collected at Screening only for WONCBP when needed; collected at [REDACTED])	Serum testosterone (males only)	

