Routine Urinalysis	
 Appearance, color Specific gravity pH, glucose, protein, blood, ketones, bilirubin, urobilinogen, nitrite, leukocyte esterase (by dipstick) Microscopic examination (if blood or protein is abnormal) Urinalysis will always be conducted by the central laboratory. 			
Pregnancy testing	
 Highly sensitive serum or urine hCG pregnancy test (as needed for WOCBP)^d 			
Other Screening Tests	
 Follicle-stimulating hormone and estradiol (as needed for WONCBP) Urine drug screen (to include at minimum: amphetamines, barbiturates, cocaine, opiates, cannabinoids and benzodiazepines). Note: The urine drug screen will be conducted by the central laboratory at Screening and the urine drug screen at subsequent visits after screening will be conducted locally at the site. In the case of a positive urine drug screen at the site, samples can be sent to the central laboratory for confirmation. Breath alcohol test 			

Abbreviations: ALP = alkaline phosphatase; ALT = alanine aminotransferase; AST = aspartate aminotransferase; BUN = blood urea nitrogen; FSH = follicle-stimulating hormone; GGT = gamma-glutamyl transferase; HbA1c = glycosylated hemoglobin; hCG = human chorionic gonadotropin; LH = luteinizing hormone; MCH = mean corpuscular hemoglobin; MCV = mean corpuscular volume; MDMA = 3, 4,-methylenedioxymethamphetamine; RBC = red blood cell; SGOT = serum glutamic-oxaloacetic transaminase; SGPT = serum glutamic-pyruvic transaminase; TSH = thyroid stimulating hormone; WBC = white blood cell; WOCBP = woman of childbearing potential; WONCBP = woman of non-childbearing potential.

^a Participants are required to fast for safety laboratory tests at the Baseline Visit (Visit 2), Week 1 (Visit 3), Week 4 (Visit 5), Week 12 (Visit 9), Early Discontinuation (Visit 10), if applicable, and Safety follow-up Visit (Visit 12). Participants are not required to fast for laboratory tests at the Screening Visit or Week 8 (Visit 7).

^b All events of ALT (or AST) $\geq 3 \times$ upper limit of normal (ULN) and total bilirubin $\geq 2 \times$ ULN ($> 35\%$ direct bilirubin) or ALT (or AST) $\geq 3 \times$ ULN and international normalized ratio (INR) > 1.5 , (if INR measured) which may indicate severe liver injury (possible Hy's Law), must be reported to the sponsor or designee in an expedited manner.

^c If alkaline phosphatase is elevated, consider fractionating.

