APPENDIX 7. LIVER SAFETY: SUGGESTED ACTIONS AND FOLLOW-UP ASSESSMENTS

Table 7: Phase 2 Liver Chemistry Stopping Criteria and Follow-up Assessments

Liver Chemistry Stopping Criteria	
ALT-absolute	ALT $\geq 5 \times$ ULN
ALT Increase	ALT $\geq 3 \times$ ULN persists for ≥ 4 weeks
Total bilirubin^{a,b}	ALT $\geq 3 \times$ ULN and total bilirubin $\geq 2 \times$ ULN ($> 35\%$ direct bilirubin)
INR^b	ALT $\geq 3 \times$ ULN and INR > 1.5 , if INR measured
Cannot Monitor	ALT $\geq 3 \times$ ULN and cannot be monitored weekly for 4 weeks
Symptomatic^c	ALT $\geq 3 \times$ ULN associated with symptoms (new or worsening) believed to be related to liver injury or hypersensitivity
Suggested Actions, Monitoring and Follow-up Assessments	
Actions	Follow-up Assessments

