
A specialist or hepatology consultation is recommended.
 
If $ALT \geq 3 \times ULN$ AND total bilirubin $< 2 \times ULN$ and INR ≤ 1.5:
 
Repeat liver chemistry tests (include ALT, AST, alkaline phosphatase, total bilirubin and INR) and perform liver chemistry follow-up assessments within 24 to 72 hours.
 
Monitor participants weekly until liver chemistry abnormalities resolve, stabilize, or return to baseline.
 
Permanently discontinue study intervention and continue participant in the study for any protocol-specified follow-up assessments.
	
Serum acetaminophen adduct assay, when available, to assess potential acetaminophen contribution to liver injury in participants with definite or likely acetaminophen use in the preceding week.
 
Liver imaging (ultrasound, magnetic resonance, or computerized tomography) and/or liver biopsy to evaluate liver disease. Provide liver imagine results via email to [contact].
 
Liver biopsy may be considered and discussed with local specialist if available:
 
In participants when serology raises the possibility of autoimmune hepatitis.
 
In participants when suspected drug-induced liver injury progresses or fails to resolve on withdrawal of study intervention.
 
In participants with acute or chronic atypical presentation
 
If liver biopsy conducted, provide liver imaging results via email to [contact].

^a Serum bilirubin fractionation should be performed if testing is available. If serum bilirubin fractionation is not immediately available, discontinue study intervention if $ALT \geq 3 \times ULN$ and total bilirubin $\geq 2 \times ULN$.

Additionally, if serum bilirubin fractionation testing is unavailable, **record the absence/presence of detectable urinary bilirubin on dipstick which** is indicative of direct bilirubin elevations suggesting liver injury.

^b All events of $ALT \geq 3 \times ULN$ and total bilirubin $\geq 2 \times ULN$ ($> 35\%$ direct bilirubin) or $ALT \geq 3 \times ULN$ and INR > 1.5 may indicate severe liver injury (**possible “Hy’s Law”**) and **must be reported to sponsor in an expedited manner and as an SAE if SAE criteria met**. The INR stated threshold value will not apply to participants receiving anticoagulants.

^c New or worsening symptoms believed to be related to liver injury (such as fatigue, nausea, vomiting, right upper quadrant pain or tenderness, or jaundice) or hypersensitivity (such as fever, rash or eosinophilia).

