10.3. Laboratory Assessments

The continuous clinical laboratory assessments (hematology, chemistry, urinalysis, [REDACTED]
 [REDACTED]) will be summarized in Safety Analysis Set using descriptive statistics by treatment group and pooled JZP150 treatment groups by scheduled visit.

Change from baseline to each post-baseline visit for clinical laboratory values is (value at the post-baseline visit) – (baseline value). If the laboratory value is missing at either baseline or a specific post-baseline assessment for a participant, change between baseline and that assessment is unknown.

Values for any of the clinical laboratory values parameters that are below or above the limit of quantification of the assay (BLQ or ALQ), will be summarized using the BLQ or ALQ threshold value; the actual reported value will be listed.

Shift tables will summarize changes in clinical laboratory results by scheduled visit with respect to the Baseline result. Laboratory values are categorized into L1, low, normal, high, or H1 based on the laboratory reference range. L1 and H1 values are predefined per the laboratory vendor alert ranges and correspond to the extreme abnormal lower and higher ranges, respectively.

Abnormal laboratory assessments deemed clinically significant by the investigator will be reported as an AE.

A listing of participants with abnormal value(s) according to the following criteria will be provided using the Safety Analysis Set:

- Any laboratory value that falls into the pre-defined low or high panic ranges (L1 or H1) per the ICON laboratory panic value chart.
- Alanine aminotransferase (ALT) or aspartate aminotransferase (AST) $\geq 3 \times$ Upper Limit of Normal (ULN) and total bilirubin $> 2 \times$ ULN
- AST or ALT $\geq 5 \times$ ULN,
- Creatinine $\geq 176 \text{ } \mu\text{mol/L}$
- Participants positive for alcohol, urine drug screen or pregnancy assessments

Jazz Pharmaceuticals
 {Statistical Analysis Plan - Protocol #}JZP150-201-02

All laboratory results, including pregnancy test, drug screen, and alcohol screen, will also be presented in participant data listings.

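### The liver stopping and dosing-suspension rules use ALT alone, although Appendix 3 defines possible Hy's Law by ALT or AST, so an AST-led case is reported but triggers neither rule

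*Protocol*

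**What the plan says.** The protocol describes possible Hy's Law in two places, with different enzymes.

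- **Appendix 3, Table 6 footnote b** begins "All events of ALT (or AST" and so admits either enzyme. At or above 3 × ULN, together with bilirubin at or above 2 × ULN (more than 35% direct) or INR above 1.5 if measured, the event must be reported to the sponsor in an expedited manner. The footnote attaches no stop or suspension.
- **Appendix 7, Table 7** has the bilirubin stopping row "ALT $\geq 3 \times$ ULN and total bilirubin $\geq 2 \times$ ULN", with the same direct-bilirubin condition. All six stopping rows are keyed to ALT. Footnote b, which gives this appendix's Hy's Law wording, begins "All events of $ALT \geq 3 \times ULN$ and total bilirubin". Footnote a and the Table 8 entry criterion are also ALT-only. AST appears in Appendix 7 only as a test to repeat.

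Both action rules cite Appendix 7 and not Appendix 3:

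- **Section 7.1.1:** "Discontinuation of study intervention for abnormal liver tests is required by the investigator when a participant meets one of the conditions outlined in" Appendix 7. A second limb covers other abnormal liver chemistries if the investigator thinks stopping is in the participant's best interest.
- **Section 10.1.9.2:** the Safety Management Team (SMT) suspends dosing if "1 or more participants on active study intervention meets Hy's Law Criteria as defined in" Appendix 7. The only other trigger there needs similar unexpected SAEs in two or more participants.

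**The concern.** The reporting rule is wider than the action rules, and the protocol gives no reason for the difference. An AST-led case can be labelled possible severe liver injury and sent to the sponsor urgently while the participant stays on drug and dosing continues across the trial, unless someone chooses to intervene.

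Hy's Law is the only suspension trigger in Section 10.1.9.2 that a single participant can meet. Section 4.1 plans no independent monitoring committee, and the internal committee reviews blinded data. Treatment runs for 12 weeks, whereas Section 4.3 describes earlier 4 mg daily dosing in patients for up to 30 days. In that setting the fixed numeric triggers matter more.

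**Working it through.** No power or error-rate calculation is involved. The check applies each rule to the same laboratory profiles.

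**Rules as written** (enzymes and total bilirubin, TB, in multiples of ULN)

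1. Expedite (Appendix 3 footnote b): (ALT ≥ 3 or AST ≥ 3) and [(TB ≥ 2 and direct > 35%) or INR > 1.5].
2. Stop (Section 7.1.1 through Table 7): ALT ≥ 5; or ALT ≥ 3 with one of these: TB ≥ 2 and direct > 35%, INR > 1.5, persistence for 4 weeks, inability to monitor weekly, or liver or hypersensitivity symptoms.
3. Suspend (Section 10.1.9.2 through Appendix 7 footnote b): ALT ≥ 3 and [(TB ≥ 2 and direct > 35%) or INR > 1.5], in a participant on active drug.

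Every route in rules 2 and 3 needs ALT ≥ 3. The set that meets rule 1 but neither rule 2 nor rule 3 is therefore:

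AST ≥ 3, ALT < 3, and [(TB ≥ 2 and direct > 35%) or INR > 1.5].

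**Illustrative profiles** (assumed values; participant on active drug; bilirubin fractionated; no anticoagulant; INR not raised where not shown)

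| Profile | ALT | AST | TB | Direct | INR | Expedite | Stop | Suspend | Stop and suspend after fix |
|---|---|---|---|---|---|---|---|---|---|
| A | 4 | 4 | 2.5 | 60% | – | yes | yes | yes | yes |
| B | 2 | 6 | 2.5 | 60% | – | yes | no | no | yes |
| C | 2 | 6 | 1.0 | – | 1.7 | yes | no | no | yes |
| D | 2.9 | 3.0 | 2.0 | 60% | – | yes | no | no | yes |
| E | 2 | 6 | 2.5 | 20% | – | no | no | no | no |
| F | 2 | 6 | 1.0 | – | 1.0 | no | no | no | no |

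B, C and D fall in the gap. Profile B shows what follows: AST 6 and TB 2.5 with 60% direct satisfy rule 1, but ALT 2 fails every Table 7 row. The Table 7 actions (immediate stop, repeat tests within 24 hours, hepatitis serology, INR, twice-weekly monitoring) are not triggered. Table 8 weekly monitoring is not entered either, because it needs ALT of at least 3. The fix brings B, C and D under both rules and leaves A, E and F unchanged.

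**Other uses of AST.** Exclusion criterion 23 in Section 5.2 pairs either enzyme with bilirubin (each above 1 × ULN). The SAP Section 10.3 abnormality listing also begins with both: "Alanine aminotransferase (ALT) or aspartate aminotransferase (AST". Its enzyme-plus-bilirubin criterion flags A, B and E. C is caught only through the separate AST ≥ 5 line. D is caught by neither line, because the SAP asks for bilirubin strictly above 2 × ULN.

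**The case against.** The strongest reply is that the protocol leaves several ways to act.

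- The second limb of Section 7.1.1 is written for liver results outside Table 7.
- Section 7.1 requires a stop for an AE that may compromise continued participation, and a clinically significant laboratory abnormality is an AE.
- Section 8.3.4 requires repeat testing of clinically significant values judged related to study drug.
- The case must be expedited to the sponsor. Section 10.1.5 lists hepatic events for committee review and allows an urgent SMT meeting, with unblinding and powers up to termination.

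These routes are real, and a stop or suspension is possible for an AST-led case. Each depends on someone's judgment, though, and none supplies the automatic trigger that an ALT-led case gets.

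Other points stand in part. The profiles are invented, so three of six is an illustration and not a rate. Profile C arises only if INR was ordered separately, because INR is not in the Table 6 panel. Entry limits are lower than on-treatment limits for ALT too, so criterion 23 shows only that the protocol elsewhere pairs AST with bilirubin.

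An ALT-only rule could be defended because AST is less liver-specific. That would support the isolated-enzyme rows. It is weaker for the combined rows, where direct bilirubin or INR must also be abnormal and Appendix 3 already accepts AST.

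**Conclusion.** The concern holds. The two Hy's Law definitions conflict, and both numeric action rules use the narrower one. An AST-led case inside the region derived above must be expedited but triggers neither the Table 7 stop nor the one-participant suspension.

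The conclusion rests on reading Appendix 7 as written, which its six ALT-keyed rows and its footnotes support consistently. The number of participants affected cannot be derived from the documents and is expected to be small. No efficacy analysis is touched. The correction is worth making because it concerns a participant-safety rule and is cheap.

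**What to change.** In Appendix 7, replace ALT with ALT (or AST) in:

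- the total bilirubin row and the INR row of Table 7;
- the monitoring block for bilirubin at or above 2 × ULN or INR above 1.5;
- footnotes a and b;
- as a conforming edit, the follow-up line that introduces the extended assessments (autoantibodies, acetaminophen adducts, imaging).

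Leave the other ALT rows and Table 8 as they are, so that an isolated AST rise still triggers nothing. Sections 7.1.1 and 10.1.9.2 need no change, because they cite Appendix 7 and would then match Appendix 3.

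As a secondary alignment, change bilirubin in the SAP Section 10.3 listing from above 2 × ULN to at or above 2 × ULN, and add INR above 1.5 where measured. That listing triggers no action, and all laboratory results are listed anyway.

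**Cost.** One protocol clarification or amendment confined to Appendix 7, plus one SAP line. Table 6 already includes ALT, AST and "Total and direct bilirubin", so no test is added; INR need not become routine. The downside is a rare extra stop or temporary suspension from a non-hepatic AST rise. The direct-bilirubin or INR condition limits this, footnote b already exempts participants on anticoagulants from the INR threshold, and creatine kinase in the same panel helps identify a muscle source.
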